2.1.7 Clinical studies with TRC105

TRC105 was administered to 50 patients with solid tumors in the context of a phase 1 first-in-human dose escalation study following a 3+3 design³⁵. The maximum tolerated dose was determined at 10 mg/kg weekly; 15 mg/kg every two weeks was equally well tolerated and also resulted in continuous serum concentrations known to saturate CD105 binding sites on proliferating endothelium. Hypoproliferative anemia was the dose-limiting toxicity: above the maximum tolerated dose, at 15 mg/kg weekly, all 3 patients that remained on study through cycle 2 developed dose-limiting grade 3 anemia, and one of the three progressed to grade 4 anemia by cycle 3. Infusion reactions, including some that were serious, were observed following TRC105 administration, usually with the initial dose. Other adverse events most commonly observed with TRC105, either alone or in combination, include fatigue, mucocutaneous telangiectasia resulting in epistaxis and gingival bleeding, flushing, and headache. Classic toxicities associated with VEGF inhibition, including hypertension, proteinuria, and thrombosis, have been seen in isolation. In fact, 3 clinical trials combining TRC105 with bevacizumab are currently ongoing (NCT01564914, NCT01648348, and NCT01332721). Multiple other phase Ib and phase II studies of TRC105 in combination with chemotherapy, with VEGF inhibitors, and as a single agent in patients with advanced prostate, sarcoma, renal cell carcinoma, choriocarcinoma, glioblastoma multiforme, and hepatocellular cancer are currently ongoing^{35,85}.

Collectively, TRC105 allows for the rational therapeutic targeting of malignant angiogenesis while sparing the cardiovascular toxicities of most contemporaneous antiangiogenic agents to which postmenopausal women with preexistent conditions may be particularly predisposed.

Although the completed clinical trials with TRC105 were not designed to assess efficacy, several patients benefitted from the investigational drug. In the phase I study where TRC105 was administered as a single agent in patients with advanced metastatic malignancies and having received a median of 4 prior lines of therapy, 6/44 patients remained progression-free for longer than 4 months³⁵.

2.1.8 Synergism between TRC105 and everolimus

In animal models, mTOR inhibition was shown to reduce the levels of VEGF and downregulate significantly the response of endothelial cells to stimulation by VEGF⁴⁵. mTOR signaling was also shown to play a key role in hypoxia-triggered smooth muscle and endothelial cell proliferation and

angiogenesis *in vitro*; this response (triggered by growth factors other than VEGF) was abrogated with mTOR inhibition⁴⁶. On the other hand, VEGF inhibition leads to reactive upregulation of endoglin⁷ and large established CD105(+) vessels lying in the core of the tumors have been shown to be insensitive to VEGF inhibitors⁸. Other preclinical studies have also demonstrated that endoglin/CD105 represents a principal escape pathway from VEGF inhibition^{7,47}. **Collectively, mTOR inhibition with anti-CD105 targeted therapy is anticipated to represent a more inclusive antiangiogenic approach as opposed to anti-VEGF therapy alone as it inhibits signaling from alternative proangiogenic factors and targets malignant angiogenesis with inherent (preexistent CD105 expression) or acquired (reactive CD105 upregulation) resistance to VEGF inhibition.**

2.1.9 Duration of neoadjuvant treatment

Most studies that prospectively evaluated preoperative hormonal therapy have limited the duration of treatment to 3-4 months^{14,15,19-21,23}. Several studies however, suggest that extending neoadjuvant hormonal therapy beyond 3-4 months is safe and associated with further and sustained reductions in the tumor size leading to a higher proportion of breast conserving surgeries^{14,86,87}. Indeed, in a prospective phase II clinical trial with preoperative letrozole treatment to maximum response, the mean time to first response was 3.9 months while the median time to maximum response was 4.2 months⁸⁷. It is noteworthy that approximately one third of the responders achieved maximum response beyond 6 months; however, very few responders were identified after 6 months and none from 8 to 12 months. The overall clinical response rate with preoperative letrozole was 76.8%⁸⁷. Similarly, in a retrospective study of 182 patients treated preoperatively with letrozole, the rate of clinical complete or partial response rose from 69.8% at 3 months to 83.5% by extending letrozole treatment up to 24 months⁸⁶. Moreover, continuing letrozole beyond 3 months increased the number of women who initially required mastectomy or had locally advanced breast cancer and subsequently became suitable for breast conserving surgery from 60% at 3 months to 72%⁸⁶.

Taken together, neoadjuvant endocrine therapy requires longer time to achieve responses as compared to cytotoxic chemotherapy. The majority of responders can be identified within the first 4 months of treatment; however, some patients require longer durations of treatment to achieve their maximum response¹⁴. In luminal breast cancer, such sustained and increased reductions in the tumor size are associated with better long-term clinical outcomes.

2.1.10 Rationale for ovarian suppression with gonadotropin-releasing hormone analogs in premenopausal women.

The IMPACT trial (Immediate Preoperative Anastrozole, Tamoxifen or Combined with Tamoxifen) established the superiority of aromatase inhibition over tamoxifen or tamoxifen + aromatase inhibition in the preoperative setting. Although the overall clinical response rate was not significantly different between the 3 arms, more patients classified as requiring mastectomy were eligible for breast conserving surgery on the anastrozole treatment arm⁴⁸. In addition, suppression of the proliferation marker Ki67 (which in itself has been shown to be predictive of favorable outcome) was statistically greater with anastrozole as compared with tamoxifen or the combination⁴⁹. Aromatase inhibitors in premenopausal women are contraindicated as they may increase gonadotropin secretion because of the reduced feedback of estrogen to the hypothalamus and

pituitary⁵⁰. To that end, in order for premenopausal women to benefit from aromatase inhibition, they should become postmenopausal through ovarian suppression with gonadotropin-releasing hormone analogs. Furthermore, ovarian suppression in combination with aromatase inhibition has been shown to be superior over tamoxifen in the adjuvant setting in premenopausal women⁸⁸ For this clinical trial goserelin subcutaneously q 4 weeks will be used to suppress ovarian function.

2.2 Correlative Studies Background

2.2.1 PI3K/AKT/mTOR pathway in breast cancer

As outlined in section 2.1.2 and 2.1.3, the PI3K/AKT/mTOR pathway can be activated by various genetic aberrations at multiple nodes along the pathway leading to resistance to or evasion from hormone blockade. Loss of PTEN increases PI3K activity and increased phosphorylation, activation, or membrane translocation of signal transducers downstream of the PI3K including Akt, mTOR, S6 kinase, and 4-EBP-1⁸⁹. Immunohistochemistry for the phosphorylated AKT (pAKT) is a surrogate for activation of the PI3K/AKT/mTOR pathway irrespective of the underlying genetic aberration; activating point mutations of signal transducers along the pathway can be captured by whole-exome sequencing.

2.2.2 Regulation of gene expression at the translational level

Over the recent years, significant progress has been made in understanding the mechanisms of transcriptional (DNA to RNA) regulation; however, little is known about the regulation of gene expression at the **translational (mRNA to protein)** level. Comprehensive analyses have shown that while mRNA and respective protein levels may correlate better than previously thought (still only at the level of $R^2=0.41$), the abundance of a protein in a cell is predominantly determined at the level of translation^{90,91}. Moreover, changes in translation have been shown to precede and be considerably more dramatic than changes in transcription in response to growth factor signaling modulation⁹². While mass spectrometry allows us to investigate translation at the protein level, it has its limitations (limitations in quantitation, incomplete and biased coverage⁹³) and small changes in the expression of critical genes that cast a large shadow at multiple cellular levels may be missed. The advent of ribosomal profiling⁹⁴⁻¹⁰⁰ (deep sequencing of the ribosome protected mRNA fragments in parallel with mRNA-sequencing) harnesses the comprehensive and unbiased nature of massively parallel deep sequencing to provide a global genomic view of ribosome occupancy across the entire exome and is a good proxy of active protein production. **There is a strong rationale in investigating ribosome occupancy across the exome as genes exert their functions by the protein products they encode.** Ribosomal profiling provides “snapshots” of which mRNAs are being actively translated and how efficiently. It serves as a proxy of protein synthesis and currently, no other technology can capture which mRNAs are being actively translated as close as ribosomal profiling. Which mRNAs are actively translated and at what efficiency is a layer of complexity in gene expression which has not been captured in the currently completed comprehensive genomic analyses in breast cancer.

3. PATIENT SELECTION

3.1 Study Population

Patients with newly diagnosed, potentially resectable (stage 2 or 3), local or locally advanced estrogen and/or progesterone receptor positive and HER2/neu negative breast cancer will be enrolled in this study

3.2 Eligibility Criteria

Patients must have baseline evaluations performed prior to the first dose of study drug and must meet all inclusion and exclusion criteria. Results of all baseline evaluations, which assure that all inclusion and exclusion criteria have been satisfied must be reviewed by the Principal Investigator or his/her designee prior to enrollment of that patient. In addition, the patient must be thoroughly informed about all aspects of the study, including the study visit schedule and required evaluations and all regulatory requirements for informed consent. The written informed consent must be obtained from the patient prior to enrollment. The following criteria apply to all patients enrolled onto the study unless otherwise specified.

3.2.1 Newly diagnosed, histologically confirmed breast cancer.

3.2.2 hormone receptor positive and HER2 negative breast cancer^{12,58}; patients with Her2/neu positive tumors irrespective of their hormone receptor status will be excluded. At least 10% of tumor cell nuclei should be immunoreactive for hormone receptors (ER and/or PR) to be deemed eligible for the study¹⁰¹. Her2/neu negative is defined as¹⁰²:

- a. Immunohistochemistry (IHC) score of 0 (no staining is observed or membrane staining that is incomplete and is faint/barely perceptible and within $\leq 10\%$ of tumor cells) **OR**
- b. IHC score of 1 (incomplete membrane staining that is faint/barely perceptible and within $<10\%$ of tumor cells) **OR**
- c. Fluorescence *in situ* hybridization (FISH) HER2/CEP17 ratio of <1.8 or average HER2 gene copy number of <4 signals/nucleus for test systems without an internal control probe.
- d. Equivocal results for Her2/neu (defined as: IHC 2+ or FISH HER2/CEP17 ratio of 1.8-2.2 or average HER2 gene copy number 4-6 HER2 signals/nucleus for test systems without an internal control probe) should prompt reflex test (same specimen using an alternative method) or order a new test (new specimen if available, using IHC or FISH).

3.2.3 Histological grade I, II or III according to the modified Bloom Richardson scale⁵².

3.2.4 Stage at diagnosis T2 through T4a-c, N0 through N2, and M0. Patients with inflammatory breast cancer or metastatic disease at diagnosis will be excluded. Patients with multicentric, multifocal, and/or bilateral disease are allowed to participate so long as all tumors meet the histologic criteria of the study.

3.2.5 Determined menopausal status. Postmenopausal status is defined according to the National Comprehensive Cancer Network¹⁰³

- a. age >60 years old **OR**
- b. prior bilateral oophorectomy regardless of age
- c. if patient <60 years old and amenorrheic for >12 months in the absence of ovarian suppression, FSH and estradiol have to be in the postmenopausal range

women who do not meet these criteria will be determined as non-postmenopausal and will require goserelin subcutaneously q 4 weeks to achieve ovarian suppression.

3.2.6 No prior treatment with therapeutic intent for breast cancer.

3.2.7 No life threatening parenchymal disease or rapidly progressing disease warranting cytotoxic chemotherapy.

3.2.8 Patients must have disease that can be measured and followed by mammogram and/or breast ultrasound (in special cases a dedicated breast MRI may be clinically indicated). The target lesion must not have been previously irradiated.

3.2.9 Resectable/Operable or potentially resectable/operable breast cancer as determined by the treating surgical oncologist.

3.2.10 ECOG performance status ≤ 2 (Karnofsky $\geq 60\%$, see **Appendix A**)

3.2.11 Life expectancy of greater than 6 months

3.2.12 Patients must have normal organ and marrow function as defined below:

- leukocytes $\geq 3,000/\text{mcL}$
- absolute neutrophil count $\geq 1,500/\text{mcL}$
- hemoglobin $\geq 10 \text{ gr/dL}$
- platelets $\geq 100,000/\text{mcL}$
- total bilirubin $\leq 2 \text{ X institutional ULN}$ (except for known Gilbert's syndrome/familial non-hemolytic jaundice)
- AST(SGOT)/ALT(SGPT) $\leq 2.5 \text{ X institutional upper limit of normal}$
- creatinine Up to 1.5 UNL, or
- creatinine clearance $\geq 40 \text{ mL/min/1.73 m}^2$ for patients with creatinine levels above institutional normal
- INR ≤ 2

3.2.13 Fasting serum cholesterol $\leq 300 \text{ mg/dL}$ OR $\leq 7.75 \text{ mmol/L}$ AND fasting triglycerides $\leq 2.5 \text{ x ULN}$. NOTE: In case one or both of these thresholds are exceeded, the patient can only be included after initiation of appropriate lipid lowering medication;

3.2.14 Age ≥ 19 years. Because no dosing or adverse event data are currently available on the use of TRC105 in patients <18 years of age⁸⁵, children are excluded from this study.

3.2.15 No bleeding from gastrointestinal ulcers or other sites of bleeding.

3.2.16 Ability to understand and willingness to sign a written informed consent document.

3.2.17 Signed informed consent obtained prior to any screening procedures.

3.3 Exclusion Criteria

3.3.1 Patients currently receiving anticancer therapies or who have received anticancer therapies within 4 weeks of the start of the investigational therapy (including chemotherapy, radiation therapy, antibody based therapy).

3.3.2 Her2/neu positive¹⁰² or estrogen and progesterone receptor negative¹⁰¹ breast cancer. Patients with triple-negative breast cancer are also excluded.

3.3.3 Metastatic breast cancer.

3.3.4 Inflammatory (T4d) breast cancer.

3.3.5 Patients may not be receiving any other investigational agents. If patients are currently part of or have participated in any clinical investigation with an investigational drug, the last administration of the investigational study should be at least 1 month prior to dosing.

3.3.6 Inoperable breast cancer even after neoadjuvant treatment as assessed by the treating surgical oncologist.

3.3.7 Undetermined or unknown menopausal status.

3.3.8 Disease that cannot be measured and/or accurately followed by mammogram and/or breast ultrasound and/or dedicated breast MRI.

3.3.9 Target lesion that has been previously irradiated.

3.3.10 History of allergic reactions, intolerance or hypersensitivity attributed to compounds of similar chemical or biologic composition to TRC105 and/or everolimus or other rapamycin analogs (e.g. sirolimus, temsirolimus).

3.3.11 Known impairment of gastrointestinal (GI) function or GI disease that may significantly alter the absorption of oral Everolimus

3.3.12 Patients must have normal organ and marrow function. Patients with any of the following abnormal parameters will be excluded:

- leukocytes <3,000/mcL
- absolute neutrophil count <1,500/mcL
- hemoglobin <10 gr/dL
- platelets <100,000/mcL

- total bilirubin >2 X institutional ULN (except for known Gilbert's syndrome/familial non-hemolytic jaundice)
- AST(SGOT)/ALT(SGPT) >2.5 X institutional upper limit of normal
- creatinine > 1.5 UNL, or
- creatinine clearance <40 mL/min/1.73 m² for patients with creatinine levels above institutional normal.
- INR ≥2

3.3.13 Uncontrolled diabetes mellitus as defined by HbA1c >8% despite adequate therapy. Patients with a known history of impaired fasting glucose or diabetes mellitus (DM) may be included, however blood glucose and antidiabetic treatment must be monitored closely throughout the trial and adjusted as necessary.

3.3.14 Uncontrolled intercurrent illness including, but not limited to, ongoing or active infection, symptomatic congestive heart failure, unstable angina pectoris, cardiac arrhythmia, or psychiatric illness/social situations that would limit compliance with study requirements. Examples of uncontrolled medical conditions include:

- a. Unstable angina pectoris, symptomatic congestive heart failure, myocardial infarction ≤ 6 months prior to start of Everolimus, serious uncontrolled cardiac arrhythmia, or any other clinically significant cardiac disease
- b. Symptomatic congestive heart failure of New York Heart Association Class III or IV
- c. Active (acute or chronic) or uncontrolled severe infection, liver disease such as cirrhosis, decompensated liver disease, and active and chronic hepatitis (i.e. quantifiable HBV-DNA and/or positive HbsAg, quantifiable HCV-RNA),
- d. Known severely impaired lung function (spirometry and DLCO 50% or less of normal and O₂ saturation 88% or less at rest on room air),
- e. Active, bleeding diathesis.

3.3.15 Chronic treatment with corticosteroids or other immunosuppressive agents. Topical or inhaled corticosteroids are allowed.

3.3.16 Patients who have received live attenuated vaccines within 1 week of start of Everolimus and during the study. Patient should also avoid close contact with others who have received live attenuated vaccines. Examples of live attenuated vaccines include intranasal influenza, measles, mumps, rubella, oral polio, BCG, yellow fever, varicella and TY21a typhoid vaccines

3.3.17 ECOG performance status >2 (Karnofsky <60%, see Appendix A)

3.3.18 Pregnancy. Women of child-bearing potential, defined as all women physiologically capable of becoming pregnant, (including female pediatric patients who are menarcheal or who become menarcheal during the treatment) must use highly effective contraception during the study and for 8 weeks after stopping treatment. Highly effective contraception is defined as either:

- Total abstinence: When this is in line with the preferred and usual lifestyle of the subject. [Periodic abstinence (e.g., calendar, ovulation, symptothermal, post-ovulation methods) and withdrawal are not acceptable methods of contraception]
- Female Sterilization: have had surgical bilateral oophorectomy (with or without hysterectomy), total hysterectomy or tubal ligation at least six weeks before taking study treatment. In case of oophorectomy alone, only when the reproductive status of the woman has been confirmed by follow up hormone level assessment
- Male partner sterilization: The vasectomized male partner should be the sole partner for that subject with the appropriate post-vasectomy documentation of the absence of sperm in the ejaculate.
- Use of oral, injected or implanted hormonal methods of contraception or placement of an intrauterine device (IUD) or intrauterine system (IUS) or other forms of hormonal contraception that have comparable efficacy (failure rate <1%), for example, hormone vaginal ring or transdermal hormone contraception. In case of use of oral contraception women should have been stable on the oral agent for a minimum of 3 months before taking everolimus

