5. TREATMENT PLAN

5.1 **Subject Selection and Registration**

At the time of study entry, the patient will be evaluated by a multidisciplinary team of medical oncologists, radiation oncologists, and surgical oncologists. Before registration, investigators are required to indicate the type of operation they intend to perform. Patients will be consented by the investigator and the coordinator of the trial. Patients will be registered in the Clinical Trials Network and Monitoring Office; the office will verify the inclusion/exclusion criteria in real time.

5.2 **Study Medications**

5.2.1 **Letrozole**

For this trial, patients will receive 2.5 mg PO daily until 1 day before surgery. The hormonal agent is commercially available and will not be provided by the study.

Description of the drug: Letrozole (Femara®) is a nonsteroidal competitive inhibitor of the aromatase enzyme system, which is responsible for the synthesis of estrogens from androgenic substrates (specifically, the synthesis of estrone from the preferred substrate androstenedione and estradiol from testosterone)⁵⁰. It is an oral agent with a half-life approximating 48 hours allowing for a once-daily administration schedule⁵⁰.

Pharmacokinetic properties: Letrozole is completely and rapidly absorbed from the gastrointestinal tract¹⁰⁵. Absorption is not affected by food. Once absorbed, it is rapidly and extensively distributed into tissues (volume of distribution at steady state is ~2 liters/kg). Letrozole is eliminated mainly by metabolism. The major metabolite, which does not inhibit aromatase, is 4'methanobisbenzotrile. This metabolite is glucuronidated and excreted primarily in the urine. Neither renal impairment (creatinine clearance < 9 ml/min) nor moderate hepatic impairment (Child-Pugh classification A and B) significantly influences letrozole pharmacokinetic parameters. Letrozole pharmacokinetics are not altered by age (range 35 to >80 years); the effects of race have not been studied¹⁰⁵.

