5.4.1.3 Pregnancy and assessments of fertility

There are no adequate data from the use of everolimus and TRC105 in pregnant women. The safety of women of childbearing capacity cannot be implied for the existing data with TRC105. Studies with everolimus in animals have shown reproductive toxicity effects including embryo-toxicity and fetotoxicity. The potential risk for humans is unknown. Everolimus should not be given to pregnant women unless the potential benefit outweighs the potential risk to the fetus. If a pregnancy occurs while on study treatment, the newborn will be followed for at least 12 months. It is not known whether everolimus is excreted in breast milk. However, in animal studies everolimus and/or its metabolites readily passed into the milk of lactating rats. Women taking everolimus should therefore not breast-feed.

Women of childbearing potential

Women of child-bearing potential, defined as all women physiologically capable of becoming pregnant, must use highly effective contraception during the study and for 8 weeks after stopping treatment. Highly effective contraception is defined as either:

- Total abstinence: When this is in line with the preferred and usual lifestyle of the subject. [Periodic abstinence (e.g., calendar, ovulation, symptothermal, post-ovulation methods) and withdrawal are not acceptable methods of contraception]
- Sterilization: have had surgical bilateral oophorectomy (with or without hysterectomy) or tubal ligation at least six weeks before taking study treatment. In case of oophorectomy alone, only when the reproductive status of the woman has been confirmed by follow up hormone level assessment

- Male partner sterilization (with the appropriate post-vasectomy documentation of the absence of sperm in the ejaculate). [For female subjects on the study, the vasectomised male partner should be the sole partner for that subject].
- Use of a combination of any two of the following (a+b or a+c or b+c):
 - a. Use of oral, injected, implanted or other hormonal methods of contraception
 - b. Placement of an intrauterine device (IUD) or intrauterine system (IUS)
 - c. Barrier methods of contraception: Condom or Occlusive cap (diaphragm or cervical/vault caps) with spermicidal foam/gel/film/cream/vaginal suppository
- In case of use of oral contraception, women should have been stable on the oral agent before taking study treatment.

Male Contraception

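### Sections 3.3.18 and 5.4.1.3 accept hormonal contraception, not limited to estrogen-free products, in women whose treatment depends on estrogen suppression, and 5.2.5 does not settle the conflict

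*Combined protocol and SAP*

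**What the plan says.** Section 3.3.18 states that women of child-bearing potential "must use highly effective contraception during the study and for 8 weeks after stopping treatment". The accepted methods include "Use of oral, injected or implanted hormonal methods of contraception" and other hormonal forms of similar efficacy, "for example, hormone vaginal ring or transdermal hormone contraception". Within that section, one listed method is enough. For the pill it adds that "women should have been stable on the oral agent for a minimum of 3 months before taking everolimus".

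Section 5.4.1.3 places the same duty on the same women with a different list. Apart from abstinence and sterilization of either partner, it asks for "Use of a combination of any two of the following (a+b or a+c or b+c". Item a is "Use of oral, injected, implanted or other hormonal methods of contraception", item b is an IUD or IUS, and item c is a barrier with spermicide.

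On treatment, Section 2.1.10 says that "in order for premenopausal women to benefit from aromatase inhibition, they should become postmenopausal through ovarian suppression with gonadotropin-releasing hormone analogs". Section 5.2.1 describes letrozole as an "inhibitor of the aromatase enzyme system, which is responsible for the synthesis of estrogens from androgenic substrates". Section 5.2.4 describes goserelin as suppressing the pituitary hormones that drive ovarian estrogen production.

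Section 5.2.5 bars, while protocol therapy is active, any hormonal therapy other than the prescribed agent. It does not mention contraceptives and does not refer to 3.3.18 or 5.4.1.3.

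**The concern.** The regimen works by taking estrogen away from a tumor selected for its hormone receptors. The eligibility and fertility text permits, in those same patients, a class of drugs that may supply estrogen. A site following the contraception rules to the letter could enroll a woman with receptor-positive cancer, give her goserelin and letrozole, and leave her on a hormonal contraceptive that nothing requires to be estrogen-free. What is at stake is the safety of that patient and whether she receives the treatment the trial intends. It is not a matter of error rates or precision.

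**Working it through.** The plan gives no figure on this point, so the check sets the sections side by side. The only arithmetic is counting.

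1. **Who is affected.** Section 3.2.2 requires ER and/or PR positivity in at least 10% of tumor nuclei. Section 3.2.5 admits women who are not postmenopausal, provided they receive goserelin. The contraception rules apply to those of them who can become pregnant.

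2. **What is accepted.** Section 3.3.18 names oral, injected, implanted, vaginal ring and transdermal methods: 5 hormonal forms. In 5.4.1.3 the permitted pairs are a+b, a+c and b+c, with a hormonal, so 2 of 3 pairs contain a hormonal method. The third pair avoids item a, but its item b still allows an IUS with no condition that it be hormone-free.

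3. **The two lists together.** A hormonal method alone meets 3.3.18 but not 5.4.1.3. With an IUD/IUS or a barrier added, it meets both. A non-hormonal IUD plus barrier also meets both: the IUD suffices in 3.3.18, and the pair is b+c in 5.4.1.3.

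4. **Whether use is meant to continue.** The 3-month stability condition for pill users, counted up to the start of everolimus, makes sense only if the pill is carried into treatment.

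5. **Whether the study drugs offset it.** As the plan describes them, letrozole acts on estrogen synthesis and goserelin on ovarian output. Neither is said to act on estrogen taken from outside.

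6. **Whether 5.2.5 resolves it.** If its exclusion means anticancer endocrine treatment only, contraceptives remain permitted. If it means any hormonal product, it forbids what 3.3.18 and 5.4.1.3 accept. Neither reading makes the three sections agree.

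7. **Whether the checks resolve it.** Screening includes FSH, LH, estradiol and a medication review (5.4.1). The principal investigator reviews baseline results (3.2), and the registration office verifies the criteria (5.1). Medication review continues on treatment, with estradiol at weeks 4, 12 and 20 in goserelin patients (5.4.2). These may find a user, but the criteria being verified allow the method and no rule tells her to stop. Under 5.6, discontinuation for estradiol in the premenopausal range is at the investigator's discretion.

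8. **The time window.** Contraception is required for 8 weeks after treatment stops. Everolimus and TRC105 stop at least 4 weeks before surgery, so from their last dose the requirement runs up to 8 − 4 = 4 weeks past surgery. Letrozole stops the day before surgery, giving 56 − 1 = 55 days past it. Section 5.4.3 ends participation at surgery, apart from follow-up of adverse events.

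**The case against.** The strongest reply is that 5.2.5 already covers this. Its list is not purely oncological, since it includes herbal medicines. One can read 3.3.18 and 5.4.1.3 as defining adequate contraception and 5.2.5 as governing which drugs may be taken. A woman can satisfy all three through abstinence, sterilization, a vasectomized sole partner, or a non-hormonal IUD with a barrier. On this view the protocol needs one clarifying sentence. The reading is plausible, but the pill-stability condition cuts against it, and a site that reads only the eligibility criteria would not reach it.

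A second reply is that 3.3.18 looks like generic wording: it mentions pediatric patients, although 3.2.14 sets a minimum age of 19. That may explain how the text arose, but it does not change what the text permits.

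A third is that exposure is limited in practice. This is a single-institution trial. A multidisciplinary oncology team evaluates each patient at entry (5.1), and the principal investigator personally oversees treatment (9.3.5). This lowers the chance of harm. It does not correct the written rule those people would apply.

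**Conclusion.** The conflict stands. Two sections expressly accept hormonal contraception without limiting it to estrogen-free products, the treatment rationale depends on estrogen suppression, and 5.2.5 leaves the matter contradictory or open. It warrants an amendment. The conclusion assumes, from general knowledge and not from the documents, that some products in the accepted classes contain estrogen.

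Only women of child-bearing potential who choose a hormonal method are affected. The plan gives no basis for estimating how many of the 26 to 38 patients that would be.

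A reader might infer more than the documents support:

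- *That a hormonal method alone satisfies the protocol.* It satisfies 3.3.18 only; 5.4.1.3 binds the same women and requires a second method.
- *That every hormonal contraceptive conflicts with the treatment.* The plan's mechanism concerns estrogen. It does not discuss progestin-only products, so excluding them, and hormone-releasing IUS, is a precaution for a population selected on ER and/or PR.
- *That the ban must cover the full 8 weeks after stopping.* The conflict shown is with study treatment, and participation ends at surgery. The documents support a ban at least until then.
- *That the trial's results are compromised.* No effect on MTD/RP2D, Ki67 or pCR/downstaging can be derived.

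**What to change.** Use one contraception list for female patients in 3.3.18 and 5.4.1.3: total abstinence, female sterilization, a vasectomized sole partner, or a non-hormonal IUD plus a barrier. The barrier should stay, because accepting an IUD alone would drop the two-method rule that 5.4.1.3 now imposes.

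Delete the oral, injected, implanted, ring, transdermal and other hormonal options, any hormone-releasing IUS, and the 3-month pill condition; the corresponding pill sentence in 5.4.1.3 then has no purpose either. State in 5.2.5 that hormonal contraceptives are prohibited during study treatment, at least until surgery. The male-contraception paragraph can stay as it is, since the female partners it covers are not patients.

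The cost is a text amendment to three sections with no new procedures. The real downside is fewer contraceptive choices alongside everolimus, which Section 5.2.2 treats as potentially teratogenic. A candidate using a hormonal method would have to switch before entry; how many would need to is unknown.
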